1.3 Rationale for this Study

TAF (co-formulated with FTC) as a fixed tablet regimen is recently licenced in Canada²⁴ and Europe. It will be unclear for treating physicians and policy makers whether all HIV+ who require TDF/FTC should be switched to TAF/FTC. It is anticipated that the cost will be similar to the current price for TDF/FTC (approximately \$1000 CAN per month), however generic TDF/FTC will soon be available and will be considerably cheaper. Statistically significant increases in BMD that are not linked to clinical outcomes will be insufficient to guide that decision.

Given sample size considerations and time to fracture endpoints, clinical validation studies are not possible. Further, it is unknown whether BMD can be improved in aging HIV+ women through cART switching. Demonstrating changes in BMD that correlate with fracture risk in a population of older HIV infected women in whom BMD data is validated with fracture risk will provide better evidence. To better understand the potential impact, in this study we also include new bone imaging modalities – trabecular bone score²⁵ and HR-pQCT²⁶ that collect further information about bone microarchitecture and bone strength to more fully understand changes in bone health. There is emerging evidence that changes detected by these new imaging modalities are independently associated with fracture risk. In previous work we showed an excess of fragility fractures in HIV infected women despite similar BMD scores.²⁷ suggesting that other parameters are important to evaluate risk. Since women experience sharp declines in BMD during menopause, the potential for improved bone health through adjustment of HIV therapy may reduce future health burdens associated with osteoporosis

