3.0 STUDY HYPOTHESIS

The primary hypothesis is that switching from TDF/FTC will improve BMD to a degree that correlates with a lower fracture risk in aging HIV+ women. We will further explore our theory that the impact is greater in those in the early stages of menopause and in those who also receive a protease inhibitor (PI) as the third ARV.

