5.0 STUDY DESIGN

This study is open-label controlled randomised, 1:1, multicentre strategic trial. Patients will be randomised to immediate vs delayed switch, with randomization allocation arranged to minimize differences between treatment groups with respect to country.

5.1 Study population:

HIV positive women who are in the peri-menopausal period or those within 10 years post menopause to capture those with greatest risk of BMD loss. As menopause typically occurs earlier in HIV + women we include those aged 40 - 60 years.³² They must be on a cART regimen containing TDF/FTC with HIV RNA <50 c/ml for at least 6 months.

5.2 Intervention:

1. Immediate switch of TDF/FTC to TAF/FTC while maintaining the third ARV agent.
2. Delayed switch of TDF/FTC to TAF/FTC at 48 weeks while maintaining the third ARV agent.

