5.3 Randomization

A computer-generated randomization list will be prepared prior to study onset by a statistician/programmer at the CIHR Canadian HIV Trials Network. Randomization will be stratified by country. Site coordinators will each be given a personal code through which they

can access the web randomization system. When a site coordinator has identified an eligible, consenting participant, s/he will access the web page, register the participant and indicate non-nominal information linked to the participant. The computer will record date and time of the transaction, the participant information and allocation, which will be issued to the coordinator.

5.4 Primary endpoint:

Comparison of the immediate vs delayed group in the % change from baseline in BMD at the lumbar spine at week 48.

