13.0 DETAILS OF STATISTICAL ANALYSIS

13.1. Sample size considerations

128 women, 64 per group, are required to detect a difference of 1% in the annual change in spine BMD at 48 weeks between those randomized to immediate switch to TAF/FTC vs those randomized to delayed switch to TAF/FTC with a two sample t test, assuming a standard deviation (SD) of 2%, 80% power and a significance level of .05. The difference of 1% is believed to be a clinically important difference to detect. The expected rate of loss in BMD in peri- and post-menopausal women is 1-3% per year.

The SD in the % change in BMD was estimated from several studies of BMD in HIV+ individuals. Yin et al ⁴⁹ compared longitudinal changes in BMD in pre and post-menopausal HIV+ and uninfected women in two separate cohorts. In the premenopausal period annual % decrease in BMD was not different in HIV+ and HIV- at the lumbar spine (LS) (-0.8 +/-2.1% vs 0.4 +/-1.9%, p=.20) and remained similar after adjusting for traditional risk factors. In the postmenopausal period annualized rates of bone loss adjusted for baseline BMD were higher in HIV+ women by 2.4 fold at the LS (-1.2 vs -0.5 %, p<.00009). In a randomized study, where participants were 90% men, mean age 40, switching from TDF to TAF containing regimens

showed a statistically significant increase in BMD (median(IQR) + 1.79 % (-.22%, 3.38%)vs 0.28% loss(-2.25,1.5%), p<.001).²¹ Another study (85 % men, median age 49) showed a mean increase in BMD of 1.5% at 48 weeks with a switch from TDF to TAF compared to a .2% loss in those continuing TDF. ²⁹A third study in persons with impaired renal function switching from a TDF to TAF containing regimen resulted in a mean increase in BMD of 2.29% at the spine and 1.47% increase at the hip.²²

13.2 Primary analysis:

Generalized linear mixed models (GLMM) will be used to estimate the effect of immediate vs delayed switch from TDF/FTC to TAF/FTC on the percent change in BMD at the spine at 48 weeks.

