In the GLMM model of percent change in BMD at the spine, each patient shall contribute two data points: the percent change in BMD at the spine at 48 weeks and the percent change in BMD at the spine at 96 weeks. A variogram will be used to determine the amount of error due to random effects and serial correlation. If random effects are the source of a significant amount of variation, terms for random intercept and random time shall be included in the model. If serial correlation is determined to be the main source of error, a single parameter will be required to model the correlation between the week 48 and week 96 values from a single patient, since there will be only two BMD values per patient after enrolment.

The model shall contain four covariates: (1) treatment arm, (2) a binary indicator for whether or not the data point corresponds to week 96, (3) the interaction between the treatment arm and the 96 week indicator and (4) a binary for country (Canada vs Italy). If sufficient woman are receiving hormone replacement therapy, an additional binary covariate may be included to capture whether or not the woman was receiving hormone replacement therapy at randomization.

The GLMM model can be expressed as follows:

$$Y = \beta_0 + \beta_1 \text{ treatment} + \beta_2 \text{ week 96} + \beta_3 \text{ treatment* week 96} \quad (1)$$

where Y is the percent change in BMD at the spine.

The hypothesis test for the primary analysis is $H_0: \beta_1 = 0$, which corresponds to the primary hypothesis of the effect of switching from TDF to TAF on percent change in BMD at the spine at 48 weeks.

13.3 Secondary analyses:

The secondary endpoints of greatest importance are: the percent change in BMD at the hip at week 48, the percent change in BMD at the hip at week 96, and the percentage change at the spine at week 96. GLMM will be used to estimate the effect of immediate switch to TAF/FTC on these outcomes

The hypothesis test for the secondary analysis is $H_0: \beta_3 = 0$ in model (1) above, which corresponds to the secondary hypothesis of the effect of switching from TDF to TAF on percent change in BMD at the spine at 96 weeks.

A similar model will be fit for the outcome of percent change in the spine. In that model, the hypothesis tests of $H_0: \beta_1 = 0$ and $H_0: \beta_3 = 0$ will both be of interest, corresponding to the secondary hypotheses of the effects of switching from TDF to TAF on percent change in BMD at the hip at 48 and 96 weeks, respectively.

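### The primary model leaves out menopausal stage, a recorded baseline factor that the protocol treats as prognostic; adding it would be a nearly free gain in precision

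*Combined protocol and SAP*

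**What the plan says.** Section 13.2 specifies the primary model: "The model shall contain four covariates: (1) treatment arm", followed by a week-96 indicator, the arm-by-week-96 interaction and country. A term for hormone replacement therapy at randomisation may be added if enough women take it. Equation (1) shows only the first three terms; country is in the text but not in the formula.

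On allocation, section 5.3 says "Randomization will be stratified by country". No other stratification factor is named.

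On menopause, section 1.3 says "Since women experience sharp declines in BMD during menopause", and section 13.1 says "The expected rate of loss in BMD in peri- and post-menopausal women is 1-3% per year". Menstrual history and antiretroviral history are both taken at screening (section 7.1), and inclusion criterion 3 requires each woman to be classed as peri-menopausal or within 10 years of menopause.

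Section 3.0 proposes that the effect of switching is larger in those in the "early stages of menopause and in those who also receive a protease inhibitor (PI) as the third ARV". Section 4.2 lists both factors as hypothesis generating. Section 13.3 examines them through interaction terms for the 48-week endpoints, comparing peri- with post-menopausal women and PI with non-PI regimens.

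**The concern.** A baseline factor that predicts the outcome adds to the residual variance of an unadjusted comparison. Entering it as a main effect removes that part of the variance and narrows the confidence interval for the treatment effect. By the protocol's own account menopausal stage is a candidate: it is tied to BMD loss, known before allocation, not balanced by design, and already needed as a two-level factor in section 13.3. It is nevertheless missing from the one model on which the primary conclusion rests.

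What is at stake is the precision of the week-48 estimate. This matters somewhat more than usual because the 128 women in section 13.1 include no allowance for the 10% dropout expected in section 13.7.

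**Working it through.** **Inputs from the documents**
- Sample size and target (13.1): "128 women, 64 per group, are required to detect a difference of 1% in the annual change in spine BMD at 48 weeks".
- Variability and error rates (13.1): "assuming a standard deviation (SD) of 2%, 80% power and a significance level of .05". Sidedness is not stated; two-sided is assumed.
- Design (5.0): "open-label controlled randomised, 1:1, multicentre strategic trial".
- Dropout before week 48 (13.7): 10%, so 128 × 0.9 = 115.2 completers, or 57.6 per arm.
- Stage-specific annual spine change in HIV-positive women (13.1): −0.8% premenopausal and −1.2% postmenopausal, from two separate cohorts. The gap is 0.4 points.

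**Assumptions that the documents do not supply**
- Stage split 50:50.
- The SD of 2% is the total SD, including variation between stages.
- Difference between stage means: 0.4, 1 or 2 points. The 0.4 is the cited pre- versus postmenopausal gap, an imperfect proxy for peri- versus post-menopausal women. The 2 is the full width of the 1–3% range and serves only as an upper bound.
- The week-48 comparison is treated as a two-sample t test, as in 13.1.

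**Step 1: reproduce the plan's figure.** The standard error is 2 × √(2/64) = 0.354, so the noncentrality is 1/0.354 = 2.83. Exact power from the noncentral t distribution is 80.1% at 64 per arm and 79.5% at 63. The 128 is reproduced. At 57.6 per arm, power is 75.8%.

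**Step 2: variance explained by stage.** For a two-level factor with proportion p and mean difference d, R² = p(1−p)d²/SD², and the residual SD is 2√(1−R²). One degree of freedom is given up.

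| Stage gap d | R² | Residual SD | Power, 64 per arm | Power, 57.6 per arm |
|---|---|---|---|---|
| Unadjusted | – | 2.000 | 80.1% | 75.8% |
| 0.4 | 0.25 × 0.16/4 = 1.0% | 1.990 | 80.5% | 76.2% |
| 1.0 | 0.25 × 1/4 = 6.3% | 1.936 | 82.6% | 78.5% |
| 2.0 | 0.25 × 4/4 = 25% | 1.732 | 90.0% | 86.7% |

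With 115 completers, an R² of about 10% is needed to bring power back to 80%.

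**Step 3: is the unadjusted test sound?** A simulation with 20,000 runs per scenario and 64 per arm compared models with and without baseline main effects (stage, plus a PI indicator at an assumed 30%). Under no treatment effect, the unadjusted model was unbiased and rejected in 4.9–5.0% of runs. Only the spread of the estimate differed between the models: 0.353 unadjusted against 0.353–0.355 adjusted at a 0.4-point gap, about 0.35 against 0.34 at 1 point, and 0.354 against 0.309 at 2 points.

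**Step 4: chance imbalance.** The SD of the between-arm difference in stage proportion is √(2 × 0.25/64) = 0.088, so its 95% range is ±1.96 × 0.088 = ±17 percentage points. At the edge of that range the estimate moves by 0.173 × d: 0.07, 0.17 or 0.35 points for gaps of 0.4, 1 and 2, against a target of 1 point. The unadjusted standard error already contains this movement, so it is the loss in step 2 seen from another side and must not be added to it.

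**The case against.** The strongest reply is that nothing here is an error and that the benefit may be close to nil. On the only stage-specific figures in the documents, stage explains about 1% of variance and power gains 0.4 points. Eligibility already narrows the menopausal range, hormone therapy may enter the model, and the interaction models in 13.3 do use stage. All of that stands. Three limits keep the point alive. The 0.4-point gap compares pre- with postmenopausal women across cohorts, so it does not measure the transition in which section 1.3 places the steep decline. The hormone therapy term is conditional and is not a substitute for stage. The interaction models are hypothesis generating and do not sharpen the primary estimate.

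The reply can also question the SD. The SDs written out in 13.1 (2.1% and 1.9%) come from premenopausal women, a single stage. If 2% is a within-stage SD, adjusted power stays at about 80.1% instead of rising to the tabulated values. Unadjusted power would then be the figure that falls: with a 1-point gap the total SD is √(4 + 0.25) = 2.06 and power is 77.7%. The tabulated values therefore depend on the assumption, but the direction of the benefit does not.

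A reader might infer more in three places, and the documents do not support it:
- *PI use drives BMD change.* Section 3.0 offers PI use only as a possible modifier of the switch effect. A modifier need not be prognostic, and no PI effect size is given.
- *Peri- and post-menopausal women differ by 2 points a year.* The 1–3% range in 13.1 is given for both groups together; putting one end on each stage is a construction.
- *Uncorrected imbalance biases the primary result.* Under randomisation it does not (steps 3 and 4).

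**Conclusion.** The point holds as a free improvement. The planned analysis is valid: its estimate is unbiased and its type I error is correct. It leaves out a baseline factor that the protocol itself presents as prognostic and already collects. The gain from adding it is about 0.4 power points at the cited 0.4-point gap, about 2.5 at 1 point and at most about 10 at the 2-point bound. These figures assume a total SD of 2%, a 50:50 stage split and 64 analysed per arm. The true R² is not in the documents, so no single value can be claimed. The downside is negligible: at the smallest gap the adjusted and unadjusted standard errors are practically equal. Because about 115 completers leave unadjusted power near 76%, even a modest gain is worth having, but only an R² of about 10% or more would make up for the dropout.

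**What to change.** In section 13.2 and equation (1):

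1. Add a fixed effect for menopausal stage at screening, coded peri- versus post-menopausal as in section 13.3. State in one sentence how each woman is classified from the screening history, and use that baseline value throughout. Settle on this one coding. Years since menopause has no value for peri-menopausal women and would leave a choice open in the primary model.
2. Report the model without the stage term as a sensitivity analysis.
3. Write the country term, already listed as covariate (4), into equation (1) so that formula and text agree.

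A main effect for PI use is optional, since the protocol gives no prognostic rationale for it.

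The cost is one degree of freedom and a few lines of SAP wording. No new data are needed. The change should be made before outcome data by arm are seen; in an open-label trial, a covariate added after an imbalance has been noticed would be hard to defend.

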Interactions terms will be used to determine if the effect of switching from TDF/FTC to TAF/FTC on 48 week endpoints varies between peri and post-menopausal women or according to whether a protease inhibitor is used as the third ARV.

Other secondary endpoints such as the change in TBS at the hip, the proportions of patients with viral load < 50 copies/mL and the mean eGFR at 48 and 96 weeks will be summarized over time by treatment group to provide preliminary information but will not be compared formally to avoid type 1 errors due to multiple comparisons.

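### Section 13.3 formally tests three key secondary BMD hypotheses with no testing order, gate on the primary, adjustment or exploratory label

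*Combined protocol and SAP*

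**What the plan says.** **Primary test.** Section 13.2 fits a mixed model to percent change in spine BMD at weeks 48 and 96, with arm, a week-96 indicator and their interaction. The primary test is beta1 = 0, the arm difference at week 48. Section 13.1 sizes the trial for this contrast: "128 women, 64 per group, are required to detect a difference of 1% in the annual change in spine BMD at 48 weeks", "assuming a standard deviation (SD) of 2%, 80% power and a significance level of .05". That is the only significance level in the document.

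**Key secondary tests.** Section 13.3 opens: "The secondary endpoints of greatest importance are: the percent change in BMD at the hip at week 48". It adds hip at week 96 and spine at week 96. Spine week 96 is assigned the test beta3 = 0. A second model, introduced as a spine model although the hypotheses that follow concern the hip, is assigned two tests, one for hip week 48 and one for hip week 96; these "will both be of interest, corresponding to the secondary hypotheses of the effects of switching from TDF to TAF on percent change in BMD".

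**Other endpoints.** Section 13.3 ends by saying that the remaining secondary endpoints, such as TBS, viral suppression and eGFR, "will not be compared formally to avoid type 1 errors due to multiple comparisons". Section 4.2 labels the menopause-stage and third-agent questions as hypothesis generating. Neither provision covers the three BMD tests.

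**The concern.** The plan has two ways of limiting what may be claimed from extra comparisons: descriptive reporting and a hypothesis-generating label. It applies neither to the three tests most likely to be reported as evidence of bone benefit, and no other rule fills the gap.

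The case that matters is a non-significant primary with one nominally significant result at the hip or at week 96. Nothing in section 13 says whether that result supports a conclusion or is exploratory, so the decision would be made after the data are seen. Section 4.1 adds to the uncertainty. It lists whether any improvement continues or stabilises in the year after switch under primary objectives, while section 13.3 treats spine week 96 as secondary.

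**Working it through.** **1. Reproduce the plan's figure and settle sidedness.** Inputs from section 13.1: difference 1%, SD 2%, power 80%, level .05; 1:1 allocation from section 5.0.

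- Normal approximation, two-sided: n per group = 2 × (1.960 + 0.842)² × 2² / 1² = 62.8, so 63.
- Two-sample t test, two-sided: 63.8, so 64 per group and 128 in total. Power at 64 per group is 80.1%.
- Two-sample t test, one-sided .05: 50.2 per group, which does not match.

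The stated 128 reproduces, and it implies that the primary .05 is two-sided.

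**2. Count the tests.** One primary (spine week 48) and three key secondaries (hip week 48, hip week 96, spine week 96). The count of three reads the second model in 13.3 as a hip model, which its stated hypotheses require.

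**3. Error rate if independent.** Assume two-sided .05 per secondary test and all three nulls true:

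1 − (1 − .05)³ = 1 − .857 = 14.3%. The Bonferroni upper bound is 3 × .05 = 15%.

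**4. Error rate under correlation.** The tests share women, sites and visits, so they are correlated. The documents give no correlations, so these are assumptions: week 48 to week 96, 0.3 to 0.85; spine to hip, 0 to 0.7; ratio of week-96 to week-48 SD, 1.0 or 1.4. Joint normal estimates were simulated with 2,000,000 draws per setting and critical value 1.96. Selected settings:

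| SD ratio | Week 48–96 corr. | Spine–hip corr. | As written (beta1 hip, beta3 hip, beta3 spine) | Week-96 tests as arm differences at week 96 |
|---|---|---|---|---|
| 1.0 | 0.3 | 0 | 13.4% | 14.0% |
| 1.0 | 0.3 | 0.7 | 11.9% | 12.7% |
| 1.0 | 0.5 | 0.5 | 12.9% | 12.9% |
| 1.0 | 0.8 | 0.7 | 12.6% | 10.9% |
| 1.0 | 0.85 | 0.7 | 12.7% | 10.5% |
| 1.4 | 0.7 | 0 | 14.2% | 12.9% |

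Over these settings the rate runs from about 10.5% to 14%. As a stress case, a common correlation of 0.9 among all three tests still gives 8.4%.

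**5. Check what the week-96 tests test.** In model (1) the arm difference is beta1 at week 48 and beta1 + beta3 at week 96. So beta3 is the change in the arm difference between the two visits, not the week-96 effect. Section 8.3 gives all participants TAF/FTC from week 48. Suppose the week-48 difference is the design value of 1% and the delayed arm then catches up fully: beta1 = 1, beta3 = −1 and the week-96 difference is 0. A test of beta3 = 0 should then reject although the arms no longer differ. If instead the 1% difference persists, beta3 = 0 and the week-96 difference is 1, which the test of beta3 cannot show. A testing order cannot be applied until this contrast is named.

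**The case against.** The best defence is that the plan already controls multiplicity where it counts. There is one primary test and, by section 13.4, no interim analysis. The long endpoint list in section 5.5 is cut to three formally tested BMD outcomes, expressly because of type 1 error. Whether a few named secondary tests also need a gate in a single-primary strategy trial is partly convention. This is real partial control and deserves credit, but it does not say how the three remaining tests are to be read.

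Some stronger readings are tempting, and the documents do not support them:

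- A reader might infer that the plan breaks a promised 5% error rate. It makes no such promise across the secondaries, and .05 per secondary test is an inference from section 13.1.
- A reader might infer that the primary result is compromised. It is not: additional secondary tests leave the test of beta1 at its own level.
- A reader might want one figure for the error rate. Anything other than the independence value depends on correlations that the documents do not give.
- A reader might infer that the sponsor intends to claim benefit from a secondary result after a failed primary. No passage says so, and section 1.3 states that significant BMD gains not linked to clinical outcomes would be insufficient to guide the switching decision.

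It can also be said that section 4.1 makes the later question conditional, since it asks about improvements already observed. That is the wording of an objective, not a testing rule, and it does not touch hip at week 48.

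**Conclusion.** The gap is real but confined to the secondary family. Three formal tests have no stated rule for interpretation, in a section that gives multiple comparisons as its reason for not testing other endpoints. The chance of at least one false positive among the three is 14.3% if independent and roughly 10.5% to 14% under the assumed correlations. These figures require two-sided .05 per test and all three nulls true. The defect is silence, not a breached commitment. The undefined week-96 contrast belongs to the same repair. The point should be addressed before the data are analysed, but it does not threaten the primary conclusion.

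**What to change.** Amend section 13.3 in this order.

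1. State that the week-96 effect at each site is the arm difference at week 96, beta1 + beta3 in model (1), and test that contrast. Report beta3 as an estimate of how the difference changes after the delayed arm switches.
2. Correct the sentence introducing the second model from spine to hip.
3. Add a fixed sequence, each step two-sided at .05: spine week 48 (primary), hip week 48, spine week 96, hip week 96. Stop at the first non-significant result. Report every later contrast as an estimate with a 95% confidence interval, labelled exploratory.

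Hip at week 48 comes second because it is the only other contrast measured while the arms are assigned different drugs; by week 96 the comparison is immediate against delayed switch. The sequence holds the chance of any false positive across all four tests at .05 or less, and the primary keeps its full .05.

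The cost is a few sentences, with no extra patients, data or visits. The downside is that a nominally significant hip or week-96 result after a failed earlier step can be reported only as exploratory. Labelling the three tests exploratory without a sequence would remove the ambiguity but give up any confirmatory reading of outcomes that the plan ranks highest among its secondaries.

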4.0 STUDY OBJECTIVES

4.1 Primary objectives:

To determine if:

1. Switching HIV+ women on TDF/FTC to TAF/FTC increases BMD at the spine at 48 weeks relative to those who continue TDF/FTC
2. To determine if any observed improvements continue or stabilize in the year after switch.

4.2. Hypothesis generating objectives:

To determine if the effect of switching from TDF/FTC to TAF/FTC on BMD varies by stage of menopause and by third ARV.

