5.5 Secondary endpoints

We will compare changes between the immediate and delayed group from data collected at screening or baseline and weeks 48 and 96.

% change from baseline in BMD at lumbar spine at 96 weeks

% change from baseline in BMD at hip at 48 weeks

% change from baseline in BMD at hip at 96 weeks

Changes in Bone architecture as determined by Trabecular bone scan (TBS)²⁵ and HRpQCT²⁶

Changes in 10 year fracture risk determined by country specific FRAX calculator³³

% with undetectable viral load HIV-1 RNA as per current assays. (This **may be** < 50/ml, < 40/ml or viral load not detected)

Change from baseline in geriatric functional measures: frailty, performance and balance

Change from baseline in muscle quality: Sarcopenia – grip strength measured by a Dynamometer and fat free mass measure (from the DXA)

Change from baseline in lipid values and Framingham cardiovascular risk scores

Changes in renal tubular and glomerular function: eGFR, Cr, urine alb/cr and protein/cr, glucosuria

Safety (clinical and laboratory adverse events)

Changes in biomarkers of inflammation, coagulation and bone metabolism

Tolerability (EuroQoL questionnaire)

5.6 Justification of Endpoints:

Primary Endpoint: BMD assessment with dual energy x-ray absorptiometry (DXA) is well established for the diagnosis of osteoporosis and for fracture risk assessment in postmenopausal women⁷. For BMD measurements to be clinically useful, they are expressed in comparison with

established normative databases. BMD is expressed as a numerical value (g/cm²). Change in BMD is considered a valid intermediate end point for efficacy of fracture risk reduction⁷. To inform the site and timing of the primary endpoint, data from studies of bisphosphonates (a major therapy for osteoporosis) was used in which the increase in BMD is greatest at the lumbar spine, with one half of the gain of BMD achieved within 6–12 months followed by a lower increase over subsequent years³⁴

Secondary Endpoints: New imaging modalities are increasingly incorporated into studies of osteoporosis to gain more detailed information on bone strength.

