8.3 Follow-up Visits for Participants

These will occur at weeks 4, 12, 24, 36, 48, 52, 60, 72, 84 and 96. At weeks 4, 12, 24, 36, 52, 60, 72, and 84, the participants will have routine investigations as per the study site, and will complete targeted physical exams. **Complete** physical exams, labwork as outlined in the schedule of Assessments on pages 25 – 26, and FSH (if premenopausal) will be required at weeks 48 and 96. Adverse events will be captured at each study visit as will any changes in clinical conditions or medications. Pill counts of returned study drug except week 52 will also be captured. The accepted windows around study visits are +/- 7 days. The procedures will last about 60 minutes.

If they agree, participants will continue to be followed even if they decide to stop the study medication

At weeks 48 and 96 all participants will complete the study imaging, collection of plasma specimens for marker banking, quality of life questionnaires, FRAX score as determined by country specific FRAX calculator, Framingham cardiovascular risk score, and geriatric measures as above. The additional procedures will last

approximately 30 minutes plus imaging time. The imaging is to be scheduled within 4 weeks of these visit dates.

Drug dispensation will be done every 3 months during the regular visits at W0, 12, W24, W36, W48, W60, W72, and 84. At week 48, all participants will receive open label TAF/FTC.

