13.4. Interim analysis: no interim analyses are planned

13.5 Feasibility: The number of women on TDF/FTC aged 45-55 at UHN, MLMC, Modena and Milan are 48, 114, 105 and 80 respectively, for a total of 347. We expect that 90% (n=312) will be eligible and of those, that 80% (n=250) women would agree to participate. In addition each of the additional four Canadian sites have agreed to recruit between 5-10 participants. Therefore, it should thus be feasible to recruit the required 128 women within 12 months.

13.6 Timeline: 6 months for start- up and ethics approval, 12 months for enrollment; 24 months for follow-up; 6 months for analysis/write-up

13.7. Loss to follow-up: We expect that 10% of randomized patients will drop out before 48 weeks. Primary analyses will be conducted assuming data are missing at random. Pattern mixture models and selection models will be used as sensitivity analyses to determine the range of possible treatment effects under the assumption of not missing at random.⁵⁰

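### The week-96 spine and hip tests are placed on β3, which is the change in the arm difference between weeks 48 and 96; the week-96 arm difference is β1+β3

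*Combined protocol and SAP*

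**What the plan says.** Section 13.2 fits one model to two values per woman, the percent change in spine BMD at week 48 and at week 96:

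Y = β0 + β1·treatment + β2·week96 + β3·treatment·week96

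The time covariate is "a binary indicator for whether or not the data point corresponds to week 96". Country is a further main effect, and hormone replacement therapy may be added as another. Section 13.2 assigns β1 = 0 to the primary week-48 hypothesis.

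Section 13.3 then assigns β3 = 0 to the "secondary hypothesis of the effect of switching from TDF to TAF on percent change in BMD at the spine at 96 weeks". For the hip it assigns β1 = 0 and β3 = 0 to the "effects of switching from TDF to TAF on percent change in BMD at the hip at 48 and 96 weeks, respectively". The sentence that introduces the hip model names the wrong site ("A similar model will be fit for the outcome of percent change in the spine"), but the sentence after it makes clear that the hip is meant.

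Section 5.5 defines the week-96 spine endpoint as the percent "change from baseline in BMD at lumbar spine at 96 weeks", compared between the immediate and delayed groups, and defines the hip endpoint in the same way. Section 8.3 states: "At week 48, all participants will receive open label TAF/FTC". No section specifies a test of β1+β3.

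**The concern.** With week 48 as the reference visit, an interaction coefficient measures how much the arm difference changes by week 96. It does not measure the difference at week 96. The two hypotheses coincide only if the week-48 difference is zero, and that is the null hypothesis the trial is designed to reject.

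Because the delayed arm also switches at week 48, catch-up is a natural scenario, and it is where the mismatch misleads most. If the delayed arm catches up fully, the stated test tends to report a negative 96-week effect when the arms are equal. If it catches up partly, the estimate carries the wrong sign while the immediate arm is still ahead. If the early benefit persists in full, the test has nothing to find. Spine and hip at week 96 belong to the small set of secondary endpoints that section 13.3 tests formally, so the error would reach the reported results.

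**Working it through.** **What the coefficients mean.** Take immediate = 1 and delayed = 0 (the plan does not state the coding; reversing it flips all signs together).

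| | Week 48 | Week 96 |
|---|---|---|
| Delayed | β0 | β0+β2 |
| Immediate | β0+β1 | β0+β1+β2+β3 |
| Difference | β1 | β1+β3 |

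Hence β3 = (week-96 difference) − (week-48 difference). Main effects for country or hormone therapy cancel from these differences. A large simulated data set confirms the reading: true differences of 1 and 0 at weeks 48 and 96 give estimates β1 = 1.00 and β3 = −1.04; true differences of 1 and 1 give β1 = 0.98 and β3 = 0.03.

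**The plan's own figure.** Section 13.1 gives a 1% difference, SD 2%, 80% power, a 5% level and a two-sample t test. Taken as two-sided, these require 63.77, so 64 per arm (128 in all), with power 0.801. The plan's sample size is reproduced.

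**Inputs for the size of the error**
- From the plan, for the spine: week-48 difference 1%, SD 2%, 64 per arm. Section 13.7 adds "We expect that 10% of randomized patients will drop out before 48 weeks", so 64 × 0.9 = 57.6, taken as 57 per arm.
- Assumed, because the documents do not give them: correlation ρ between the two visits of 0.3 to 0.7; week-96 SD of 2%, or 2.83% if the variance doubles (√8); two-sided 5% tests; complete pairs; no further loss after week 48.

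**Formulas**
- SE(β3) = √[2(V48 + V96 − 2ρ·SD48·SD96)/n]
- SE(β1+β3) = √[2·V96/n]
- Rejection probabilities come from the noncentral t distribution with 2n − 2 degrees of freedom.

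With n = 64, both SDs 2 and ρ = 0.5: SE(β3) = √[2(4 + 4 − 4)/64] = 0.354. At ρ = 0.3 and 0.7 it is 0.418 and 0.274. SE(β1+β3) = √(8/64) = 0.354.

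**Results.** Ranges run over ρ = 0.3 to 0.7, with a true week-48 difference of 1% throughout.

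| Per arm, week-96 SD | Full catch-up (week-96 difference 0, β3 = −1): β3 test rejects | Half catch-up (week-96 difference +0.5, β3 = −0.5): β3 test rejects | 1% persists (β3 = 0): β3 test rejects | 1% persists: β1+β3 test rejects |
|---|---|---|---|---|
| 64, 2% | 66% to 95% | 22% to 44% | 5% | 80% |
| 57, 2% | 61% to 93% | 20% to 40% | 5% | 75% |
| 64, 2.83% | 48% to 79% | 16% to 28% | 5% | 51% |
| 57, 2.83% | 44% to 75% | 15% to 26% | 5% | 46% |

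Under full catch-up the correct rejection rate for a week-96 comparison is 5%, and the β1+β3 test has that rate. Under half catch-up, rejections by the β3 test are mostly in the wrong direction, because the true week-96 difference is +0.5 and β3 is −0.5.

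**The case against.** The best defence is that the intended comparison is already in the plan. Section 5.5 defines the week-96 endpoints as comparisons between arms of change from baseline, and section 13.3 opens by saying that the mixed model will estimate the effect of immediate switch on them. On that view the two hypothesis lines are a slip, the primary analysis is untouched, and an analyst would estimate the right quantity. In addition, β3 is a legitimate quantity: it shows whether the gap changes once the delayed arm has switched.

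The defence does not remove the fault. The two null hypotheses are explicit, the same assignment is made for spine and hip, and β1+β3 appears nowhere, so an analyst who follows the text runs the wrong test. Measuring the week-96 value from week 48 would not rescue it either: the week-96 arm difference in this model would still be β1+β3.

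Some limits stand:
- The percentages apply to the spine. The plan gives no SD or target difference for the hip, where only the algebra carries over.
- The catch-up figures depend on the assumed correlation and week-96 SD. Only the 5% rate under a persisting difference does not.
- Section 13 is part of the protocol, so the correction may need a protocol amendment and ethics review.

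**Conclusion.** The concern holds. As written, section 13.3 tests the change in the arm difference and labels it the effect at 96 weeks, for both spine and hip. This follows from the plan's own equation and coding and needs no outside figure.

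For the spine, full catch-up makes the stated test reject in 44% to 95% of trials across the settings examined, where 5% would be correct. If a 1% benefit persists in full, it rejects in 5%, against 46% to 80% for the correct contrast.

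The label also describes the contrast wrongly. Once everyone takes TAF/FTC after week 48, the week-96 comparison is immediate versus delayed switch, not TAF versus continued TDF. The week-48 primary test, the sample size and the data collection are not affected. The correction should be made before the analysis.

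**What to change.** In section 13.3:
- For spine and for hip, replace the week-96 hypothesis with H0: β1+β3 = 0, reported with a 95% confidence interval and described as immediate versus delayed switch at week 96.
- Describe β3 as the change in the arm difference from week 48 to week 96, if it is kept.
- Name the hip, not the spine, in the sentence that introduces the hip model.

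The same fitted model supplies β1+β3 and its standard error. The cost is wording, with a protocol amendment if the approval rules require one; there are no new data and no change to the primary test or sample size.

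One separate point, not caused by this error, can be settled in the same edit. Section 13 links no contrast to the second primary objective in section 4.1 ("To determine if any observed improvements continue or stabilize in the year after switch"), and the plan should name one. An option is the immediate arm's change from week 48 to week 96, β2+β3, with a 95% confidence interval, reported as a descriptive and uncontrolled estimate.
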